The authors conducted the first systematic, prospective study of resident-to-resident elder mistreatment (R-REM) in nursing homes and have developed novel methodology to identify the phenomenon. Data demonstrated that (1) R-REM is highly prevalent, (2) case finding methodology is greatly enhanced by meaningful participation of front line staff, and (3) paradoxically, higher functioning residents may be at greatest risk for involvement in R-REM (e.g., residents who are ambulatory and capable of wandering as opposed to those who are in the last stages of dementing illness). Additionally, funded by the New York State Department of Health

dementia grants program we developed a three module-program targeting front line staff to implement best practices related to R-REM in long-term services and support (LTSS) settings. Using an experimental design, we tested the intervention in nursing homes. Evaluation of longitudinal outcomes showed significant increases in staff knowledge post training, controlling for pre-training levels for the intervention group and of increased recognition of R-REM, and longitudinal reporting in the intervention as contrasted with the usual care group.¹⁸ Additionally, falls, accidents and injuries were reduced.¹⁹ These findings have important implications for assisted living residences (ALRs) where residents typically have cognitive impairment with better mobility and less staff to intervene in R-REM. The state survey process is also less uniform in ALRs (in comparison to nursing homes) and has not addressed R-REM.

Objectives

The goal of the project is to evaluate a training program for staff that enhances identification and intervention with respect to episodes of resident-to-resident elder mistreatment (R-REM). The hypotheses corresponding to the specific process outcome aims (1 & 2) and primary distal outcome (aim 3) for which the study was powered are:

Aim 1 (A1). Enhance staff knowledge of R-REM

Hypothesis 1: Staff knowledge related to R-REM and R-REM treatment will increase after training.

Aim 2 (A2). Enhance staff recognition, reporting and care planning related to R-REM

Hypothesis 2: Due to the heightened awareness as a result of training, the frequency of reported R-REM in the intervention group will increase, relative to the comparison group after training.

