Aim 3 (A3). Evaluate the impact of the staff intervention on resident falls, accidents and injuries and on quality of life using a prospective experimental design that derives information from five sources: (1) resident interviews (2) staff informants (3) observational data (4) chart and (5) incident/accident report data.

Primary Hypothesis: The frequency of falls, accidents and injuries will decrease in the

intervention group, relative to the comparison group after implementation of the training intervention.

Secondary Hypotheses: 1. Resident quality-of-life as measured by affective state will improve in the intervention group, relative to the comparison group after implementation of the training intervention.

2. Resident behavior problems will decline in the intervention group, relative to the comparison group after implementation of the training intervention. Resident behaviors will mediate the relationship between the intervention and the falls/accidents/injuries outcome.

Trial design

This is a pragmatic, prospective, cluster randomized trial (facility level) design with three waves of data collection (baseline, 6- and 12-months) at 12 assisted living facilities in two New York regions. There will be three levels of clustering: facilities within regions, units within facilities and repeated measures on residents within units, with the regions fixed. On a rolling basis, six facilities will be selected at random and recruited in New York City and the nearby suburban counties (downstate region). Six facilities in the upstate New York region of Rochester will also be randomly selected. Three facilities in each region will be randomized to usual care or to the intervention on a 1:1 ratio. Facilities allocated to the usual care group will receive the intervention after completion of their 12 month data collection.

Methods: Participants, interventions and outcomes

Study setting

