This measure was based on the Shift Coupon, a form originally designed by nursing staff to provide a “quick, easy, anonymous, and non-threatening method to report adverse events,”²¹ and is in the form of a small note pad. BRDSs are intended to measure recognition and capture real time R-REM events. Hypothesis 2, regarding enhanced R-REM recognition will be examined with a Chi-square analysis comparing counts of BRDS reports from experimental and comparison facilities captured over time, and treated as binary incidents. Reporting implementation will be examined by evaluating the differences between experimental and comparison group staff reports of R-REM, collected over three waves. Individual R-REM reporting will be determined by counting whether any of the staff-reported R-REM indicators are positive. The object of this analysis is not to identify individuals and perpetrators, but to examine the reported events. In modeling R-REM events, a Poisson regression of count data will be performed.

Aim 3: Primary level-4 evaluation of distal outcomes: Summary of the sources of data for determining falls/accidents/injuries and incidents of R-REM: The data used for evaluation of the primary distal outcome and for R-REM reports include (a) self-report among those residents who are capable, (b) Accident and Incident Reports, (c) resident record review, (d) observational data, including the BRDS, and (e) reports from staff. In addition, an environmental evaluation will occur. Data for falls and injuries will be collected via chart review, staff report and residents who can self-report, and from Incident/Accident Reports on an ongoing basis. Resident and staff informant information will be collected at baseline, 6- and 12-month follow-up. Falls will be considered as binomial (any fall) and Poisson distributed (fall counts).

Sample size {14}

Power calculations are provided for the primary distal outcome: falls, including accidents and injuries, also the outcome requiring the largest sample size. Upstate it is expected that an average

of 50 residents per site will be selected for a total of 300. Downstate, the facilities are larger, and it is expected that the average size will be 125 residents or 750 total. The proposed sample size is 6 facilities and 525 residents per arm.

Using the canonical link (Logit), the generalized linear model (GLIMMIX):

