$\eta = \log(p_{ijk} / (1 - p_{ijk})) = \beta_0 + \beta_1 X_{ijk} + FU_{jk}$, where FU_{jk} is a random effect associated with facility and unit.

The formula for the sample size per group using the method of Diggle is:

$m^* = (z_{\alpha} \sqrt{2PQ} + z_{\beta} \sqrt{p_0 q_0 + p_1 q_1})^2 (1 + (n-1)\rho) / (n(p_1 - p_0)^2)$; and using the GEE method:

$m^* = \frac{(Z_{1-\alpha/2} + Z_{1-\beta})^2 (\pi_1 p_0 (1 - p_0) + \pi_0 p_1 (1 - p_1)) (1 + (n-1)\rho)}{2n\pi_0\pi_1(p_0 - p_1)^2}$. The formula below is adjusted with variance inflation factor (V_{if}) and reliability(R_{el}): $m = V_{if}m^* / R_{el}$ and

$$V_{if} = (1 + (n_e - 1)\rho_e)(1 + (n_s - 1)\rho_s n_e p_e / (1 + (n_e - 1)\rho_e))$$

where $n_s = 5$ is the average number of units in the facility, $\rho_s = 0.015$ is the ICC for facility, $n_e = 17$ is the average number of residents in the unit, $\rho_e = 0.03$ is the ICC for unit, and the reliability:

$$R_{el} = 0.95.$$

The following table assumes $\alpha = 0.05$, power $(1 - \beta) = 80\%$, $R = 0.95$ and $V_{if} = 2.5$ (With $n_e = 17$,

$ICC_{Unit} = 0.03$, $N_s = 5$, $ICC_{Facility} = 0.015$, the fall rate at follow-up: $p_0 = 33\%$ and $p_1 = 20.75\%$). Two

scenarios for ρ (the average correlation of the outcomes over waves) were posited:

Group	Fall rate P(y=1)				Diggle Method		GEE Method	
	Baseline Rate	6 Month	12 Month	Combined 6M & 12M	M ($\rho = 0.5$)	M ($\rho = 0.6$)	M ($\rho = 0.5$)	M ($\rho = 0.6$)
Intervention	37%	22%	19.5%	20.75%	404	431	399	425
Usual Care	37%	34%	32%	33%	404	431	399	425

As shown, with 525 per group, power is adequate for intent-to-treat (ITT) analyses, including all respondents. Because randomization is at the facility rather than individual level, there is the potential for imbalance on baseline variables and missing covariate data. Assuming attrition of

15% at wave 1, it is estimated that 445 per group will have at least baseline and one additional wave of data included, using the EM missing data algorithm; thus, power is adequate to detect the posited difference in fall reduction of about 12% even with attrition.

Recruitment

All residents are approached and invited to participate. For those who do not wish to be interviewed, a different or the same interviewer approaches again at another time that may be more amenable to the resident. All resident questions are addressed and interviews occur at a time and place preferred by the resident.

Assignment of interventions: allocation

Sequence generation

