Analyses for the primary hypothesis for the distal outcome: The primary analyses will examine, on an ITT basis, the differences between the usual care and intervention groups in the reduction of falls/accidents/injuries over time. Other approaches, e.g., the analysis of the “as treated” sample can result in biased estimates of the causal treatment effect due to compromised random assignment. Our primary approach to analyses is guided by our own experience,⁵⁷ and reviews.^{58,59} Depending on the level of missing data, analytic strategies (see below) can be used to address non-compliance, e.g.⁶⁰ Based on prior trials that we have coordinated, sampled from this population, 1 year attrition is between 30% and 40%; thus for 6-month data (projected attrition of 15%), the ITT analyses of all subjects will be feasible. Longitudinal analyses will include those with at least baseline and one follow-up. Sensitivity analysis will be performed using multiple imputation under different assumptions for missing data.

Because randomization is at the facility rather than individual level, imbalance may be observed on baseline variables. Preliminary analyses will be performed to determine whether the groups are balanced. Two-tailed tests of significance will be performed. Binomial tests are to be conducted on dichotomous variables, Poisson tests on nonbinomial (e.g., count) data, and *t* tests on ordinal data, adjusting standard errors for clustered data within facilities; *p* values are reported because the design does not permit randomization at the level of the individual.

Effect on likelihood of falls/injuries/accident reduction:

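### Capture of the primary falls/accidents/injuries outcome may differ by arm: its sources may include the BRDS and do include staff report, and no check by source is planned

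*Combined protocol and SAP*

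**What the plan says.** Under Outcomes, Aim 3, a single list of sources serves two purposes: the primary distal outcome and the R-REM reports. It ends with "d) observational data, including the BRDS, and (e) reports from staff". A later sentence deals with falls and injuries alone: "Data for falls and injuries will be collected via chart review, staff report and residents who can self-report", together with Incident/Accident Reports. That sentence does not name the BRDS.

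Hypothesis 2, under Objectives, states the intended effect of training on reporting: "Due to the heightened awareness as a result of training, the frequency of reported R-REM in the intervention group will increase". Under Outcomes, Aim 2, BRDS counts are compared between arms to test it.

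Four other places matter:
- Intervention description: training is delivered after baseline in intervention facilities, and only after the 12-month data in usual care. Module 2 discusses bruises, cuts and fractures as possible signs of abuse. Module 3 practises BRDS completion and covers reporting rules.
- Observational Data, item B: both arms receive BRDS pads, intervention staff at module 3 and usual-care staff when the unit opens.
- Concealment mechanism and Blinding: facilities are told their assignment; research staff are blinded as far as possible.
- Statistical methods: the primary model controls for baseline falls. The sensitivity analyses concern missing data, plus GEE for the secondary outcomes. None is by data source.

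**The concern.** A process measure that the intervention is designed to raise should not also help to define the outcome that the intervention is expected to lower. On one reading of the Aim 3 text, it does. Even on the other reading, staff report remains a source, and it comes from people trained in one arm only.

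Injuries belong to the primary composite, and the training teaches staff to look for them as evidence of R-REM. A fall or injury arising from an R-REM event could therefore be recorded more completely in the intervention arm. The comparison would then mix how often events happen with how often they are recorded. A true reduction would look smaller than it is, and a null or unfavourable result could not be told apart from success on Aim 2. Because the shift would begin after baseline, the baseline falls covariate carries no information about it.

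**Working it through.** **Inputs** (Sample size and Statistical methods sections): follow-up event rates 33% (usual care) and 20.75% (intervention), so a difference of 12.25 points; alpha 0.05 with "Two-tailed tests of significance will be performed"; power 80%; reliability 0.95; variance inflation 2.5, taken as stated; two follow-up waves; correlation 0.5 or 0.6, described as "scenarios for ρ (the average correlation of the outcomes over waves) were posited"; 525 residents per arm, 445 after attrition.

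**Step 1: the plan's own figures.** Diggle formula, correlation 0.5. Mean rate P = (0.33 + 0.2075)/2 = 0.26875, so √(2PQ) = 0.6269. The variance sum is 0.33×0.67 + 0.2075×0.7925 = 0.3855, with root 0.6209.

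m* = (1.960×0.6269 + 0.8416×0.6209)² × 1.5 / (2 × 0.1225²) = 153.3

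m = 153.3 × 2.5/0.95 = 403.4, which rounds up to the plan's 404. Correlation 0.6 gives 430.3 (plan: 431). The GEE formula gives 398.0 and 424.5 (plan: 399 and 425). All four figures reproduce. All four also assume equal capture in both arms: the 0.95 reliability factor is one multiplier on the total and does not vary by arm.

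**Step 2: introduce unequal capture.** Let r be capture in the intervention arm relative to usual care. The documents give no value for r, so every value below is an assumption. The observed intervention rate is 20.75% × r. The effective number per arm is 445 × (0.95/2.5) × 2/(1 + 0.5) = 225.5. Power is Φ(d/SE − 1.96), where d is the observed difference and SE = √(variance sum / 225.5).

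For r = 1: SE = √(0.3855/225.5) = 0.0414, d/SE = 2.96, power 84%.

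**Step 3: which values of r fit the mechanism?** If only R-REM-linked events are affected, r = 1 + (share of residents with an event whose events are all R-REM-linked) × (relative rise in capture of those). A 10% share with a 20% rise gives 1.02. A 20% share with a 20% rise gives 1.04. Reaching 1.10 needs, for example, a 20% share with a 50% rise.

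| r | Observed intervention rate | Observed difference (points) | Power, correlation 0.5 | Power, correlation 0.6 | Apparent excess if no true effect (points) |
|---|---|---|---|---|---|
| 1.00 | 20.75% | 12.25 | 84% | 82% | 0 |
| 1.02 | 21.2% | 11.8 | 81% | 79% | 0.7 |
| 1.04 | 21.6% | 11.4 | 78% | 76% | 1.3 |
| 1.05 | 21.8% | 11.2 | 77% | 74% | 1.7 |
| 1.10 | 22.8% | 10.2 | 68% | 65% | 3.3 |

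The last column is 33% × (r − 1). Using the Diggle null variance instead lowers each power by about half a point. With all 525 per arm and correlation 0.5, power is 90% at r = 1, 83% at r = 1.05 and 75% at r = 1.10. The planned difference vanishes only at r = 0.33/0.2075 = 1.59.

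**The case against.** The strongest reply is that none of this is shown to happen. Hypothesis 2 predicts more reported R-REM, not more reported falls, and no section says that training aims to raise fall reporting. The BRDS items described (people involved, actions, place, cause, staff response) include no fall or injury field, and the falls-specific sentence leaves the BRDS out. The Background reports that in the earlier nursing-home trial R-REM reporting rose while falls, accidents and injuries went down. Facilities know their assignment, so trained staff could also under-record falls, which would favour the intervention. For the binary outcome, an extra staff report changes nothing if another source already shows an event for that resident.

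Most of this stands. A reader might infer that ascertainment does differ by arm and does bias the trial against the intervention. The documents support only that it may, with dilution the likelier direction if reporting spills over to falls and injuries. A reader might also apply a 20% rise in capture to every event, which would give 48% power. That does not match a mechanism confined to R-REM-linked events.

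Two things are left. The earlier trial shows that dilution need not hide a real effect, not that there was none. And the joint list, as written, lets the BRDS in, with no rule for combining sources and no analysis that would reveal a difference by arm.

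A stronger remedy, removing the staff informant from the primary outcome, is not clearly better. Chart entries and incident reports are staff-written too, and Aim 2 also targets care planning. The extended interview is expected to reach only about 70-80% of residents, so events could be lost in those who cannot self-report.

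**Conclusion.** The concern holds as a risk that the plan leaves unaddressed; it is not a demonstrated bias. Whether the BRDS counts toward the primary outcome is ambiguous, because the two source statements differ. Staff report counts on either reading. The reporting shift, if it reaches falls and injuries, begins after baseline and is invisible to the planned model.

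The likely effect is modest. At 445 per arm and correlation 0.5, it costs about 3 to 6 points of power if only R-REM-linked events are affected (overall rise of 2-4%), and about 7 to 16 points if capture of all events rises by 5-10%. Planned power after attrition is only a few points above 80%, so even the narrower range can take it below target. These figures rest on assumed capture ratios and on the plan's own large-sample formulas and variance inflation. The documents do not support reading them as an estimate of what will happen.

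**What to change.** 1. State under Outcomes, Aim 3 that the BRDS is an Aim 2 process measure and does not count toward the primary falls/accidents/injuries outcome. Separate the joint source list into one list for that outcome and one for R-REM, and say how the sources for the primary outcome combine for each resident.
2. Pre-specify a sensitivity analysis that repeats the primary model without the staff-informant report, using Accident/Incident Reports, dated chart entries and resident self-report.
3. Tabulate the outcome by source and arm at each wave. Show self-report separately: its falls question covers the past year, so at 6 months it reaches back before baseline.

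The sources are already collected, so the cost is wording and a little more analysis. A few events recorded only on the BRDS may be lost. The restricted analysis reduces dependence on trained staff but does not end it, because charts and incident reports are also written by staff. Agreement between the two analyses would be reassuring rather than conclusive.

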Statistical methods appropriate for clustered data will be used in the primary analysis to compare the groups with respect to the binary outcome. Generalized mixed effects models (MEMs) will be used to test the hypothesis that those assigned to the intervention will experience a significantly higher rate of fall/accident/injury reduction as contrasted with usual care. The outcome will be modeled as a function of intervention, time and their interaction and controlling for the baseline falls. To account for the clustered nature of the outcomes, the models will include random effects for facilities, units and subjects. The models will be fit using mixed effects logistic-regression as implemented in SAS Proc Glimmix. The appropriate covariance structure will be determined. The primary analysis will be supplemented with an exploration of the effect of baseline subject, facility and unit characteristics on the intervention effect. These results will inform generalizability of

intervention effects.

Analyses for secondary outcomes: The proposed secondary outcomes are affect, measured by the FTQ and the NIH PROMIS depression measure,^{61,62,63} and behavior. The reliability estimates of the outcomes are typically at least 0.90. Methods for analyses of treatment effects in pre-post clinical trials, in the context of missing data, have been compared.^{64,65,66,67,68,69} The primary proposed analyses will use MEMs, and a full information likelihood approach, with sensitivity analyses using generalized estimating equations (GEE).

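### The supporting Poisson analyses of fall counts and R-REM events make no stated allowance for overdispersion or time at risk, although the plan's own across-wave correlation implies overdispersed counts

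*Combined protocol and SAP*

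**What the plan says.** All references are to the combined protocol and SAP.

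- **Outcomes, Aim 3:** "Falls will be considered as binomial (any fall) and Poisson distributed (fall counts".
- **Outcomes, Aim 2:** "Individual R-REM reporting will be determined by counting whether any of the staff-reported R-REM indicators are positive". Two sentences later: "In modeling R-REM events, a Poisson regression of count data will be performed". The sentence between them says that the aim is to study the events that are reported.
- **Statistical methods for primary and secondary outcomes:** after the text on baseline balance, the plan lists binomial tests, then "Poisson tests on nonbinomial (e.g., count) data, and *t* tests on ordinal data, adjusting standard errors for clustered data within facilities". For the primary falls analysis it says "Statistical methods appropriate for clustered data will be used in the primary analysis to compare the groups with respect to the binary outcome", "The models will be fit using mixed effects logistic-regression as implemented in SAS Proc Glimmix" and "the models will include random effects for facilities, units and subjects".
- **Sample size:** the trial is powered on the any-fall proportion, 33% against 20.75%, with two scenarios (0.5 and 0.6) for the correlation of the outcome across waves.
- **Retention plans:** attrition of 15% at 6 months and up to 40% at 12 months.

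No section mentions an overdispersion check, a negative binomial or quasi-Poisson alternative, or an offset for time at risk.

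**The concern.** A Poisson model sets the variance of a count equal to its mean. Falls and aggressive incidents recur in the same people, so the variance usually exceeds the mean. Model-based Poisson standard errors are then too small by the square root of the variance/mean ratio.

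Exposure is a separate gap. Falls are gathered continuously from charts and incident reports, and a substantial share of residents will leave. Raw counts from residents observed for different lengths of time are not comparable without an offset, and a change to the standard errors does not cure that.

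For R-REM, the text moves from a 0/1 indicator per resident to a Poisson model of counts without saying which is the response.

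The primary hypothesis and Hypothesis 2 are both worded in terms of frequency. A count result speaks directly to that wording, so it should be sound even though it is only supporting.

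**Working it through.** **1. The plan's own figures.** Inputs from the Sample size section: p0 = 0.33, p1 = 0.2075, two-sided alpha 0.05, power 80%, variance inflation 2.5, reliability 0.95. The number of follow-up waves is n = 2 (6 and 12 months). The printed formulas multiplied by 2.5/0.95 give:

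| Method | rho | Recomputed | Stated |
|---|---|---|---|
| Diggle | 0.5 | 403.4 | 404 |
| Diggle | 0.6 | 430.3 | 431 |
| GEE | 0.5 | 398.0 | 399 |
| GEE | 0.6 | 424.5 | 425 |

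The figures reproduce. They rest on the binary outcome, so nothing below changes them. The plan gives no mean count, dispersion or standard error for any count analysis.

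**2. What the correlation implies for counts.** Assume that each resident has a stable fall rate, gamma-distributed with mean μ and squared coefficient of variation k, and Poisson counts given that rate. Let q = 1 − 0.33 = 0.67.

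- No fall in one wave: (1 + kμ)^(−1/k) = q, so kμ = q^(−k) − 1.
- No fall in either wave: q2 = (1 + 2kμ)^(−1/k).
- Correlation of any-fall between waves: ρ = (q2 − q²)/[q(1 − q)].
- Variance/mean of the per-wave count: φ = 1 + kμ.
- Actual size of a nominal 5% model-based Poisson test: 2[1 − Φ(1.96/√φ)].

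Example for ρ = 0.5: q2 must be 0.4489 + 0.5 × 0.2211 = 0.5595. This is met at k = 2.90, where kμ = 2.19 and φ = 3.19.

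| ρ | k | φ | √φ | Actual type I error |
|---|---|---|---|---|
| 0.2 | 0.76 | 1.36 | 1.16 | 9% |
| 0.3 | 1.29 | 1.68 | 1.29 | 13% |
| 0.5 | 2.90 | 3.19 | 1.79 | 27% |
| 0.6 | 4.21 | 5.40 | 2.32 | 40% |

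At the intervention rate of 20.75%, φ is 2.9 and 4.8 for ρ = 0.5 and 0.6. Clustering by unit and facility is not included.

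**3. Dependence on the assumed shape.** Suppose instead that a share π of residents fall at rate λ and the rest never fall. Then 1 − e^(−λ) = [0.33² + ρ × 0.2211]/0.33, π = 0.33/(1 − e^(−λ)) and φ = 1 + λ(1 − π).

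- ρ = 0.5: λ = 1.09, π = 0.496, φ = 1.55, type I error about 12%.
- ρ = 0.6: λ = 1.32, π = 0.451, φ = 1.72, type I error about 14%.

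The size therefore depends heavily on the shape. In both shapes φ is above 1.

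**4. Simulation check of the size formula.** Null data for 12 facilities × 5 units × 17 residents, assumed mean count 0.4, no clustering. At k = 2, φ = 1 + 2 × 0.4 = 1.8, for which the formula gives 14.4%; the simulation gave 14.4%. At k = 1, φ = 1.4; formula 9.8%, simulation 9.0%.

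**5. The 0/1 R-REM reading.** If the any-positive indicator (prevalence p) were fitted as Poisson, the model-based error would be 1/√(1 − p) times the true one: 5%, 12% and 20% too wide at assumed p of 10%, 20% and 30%. That is conservative.

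**6. Exposure.** At the stated attrition, 525 × 0.85 = 446 residents per arm remain at 6 months and, at worst, 525 × 0.60 = 315 at 12 months. Anyone with one post-baseline observation stays in the analysis, so days at risk will vary widely.

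**The case against.** The strongest reply is that nobody proposed model-based errors. The statistical methods section attaches facility-clustered standard errors to Poisson tests, and cluster-robust errors would also absorb variance above the mean. The sentence sits in the baseline-balance paragraph. However, it says that p values are reported, whereas the plan later says that none will be given for baseline variables, so a baseline-only reading is not secure. This stands in part: if the sentence covers the count models, the dispersion problem largely goes. Two gaps remain. Uncorrected robust errors tend to be too small with 12 facilities (at most 12 − 2 = 10 between-facility degrees of freedom, critical value 2.23 rather than 1.96), and no correction is stated. Robust errors also do nothing for unequal exposure. The subject random effect would likewise absorb stable differences between residents, but it is written for the logistic model.

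It is also fair to say that 0.5 and 0.6 are planning scenarios, not estimates. A higher value raises the required sample size, so they may have been chosen as cautious. Hence the range down to 0.2.

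Three stronger readings are tempting, and the documents do not support them:

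- **The trial's error bars are wrong.** The primary and powered analysis is logistic, on the binary outcome, and no count standard error is given.
- **Residents who leave early will be scored as low fallers.** The plan treats loss to follow-up as missing data, with multiple-imputation sensitivity analyses. What is missing is a rule for partial exposure.
- **The R-REM model contradicts the R-REM definition.** The indicator and the event count can be two variables. This is an ambiguity, and its error would run in the conservative direction.

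**Conclusion.** The point holds for the supporting analyses of fall counts and R-REM event counts only. As written, they are Poisson with no stated allowance for overdispersion and no offset. On the plan's own correlation of 0.5 to 0.6 at a 33% any-fall rate, variance/mean is about 3 to 5 under an assumed gamma frailty, and a model-based Poisson test would run at about 27% to 40% instead of 5%. At a correlation of 0.2 to 0.3 it is about 1.4 to 1.7, or 9% to 13%. A never-faller mixture at the plan's own correlation gives about 12% to 14%. All of these apply before clustering, and only if the facility-clustered errors are not meant to cover these models.

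The direction is firm and the size is not, because the documents give no count data. The change should be made, but the primary conclusion does not depend on it.

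**What to change.** 1. **Fall counts:** use a negative binomial mixed model with facility, unit and subject effects, or a Poisson model with robust, small-sample-corrected errors. Add a log(time at risk) offset, and define time at risk for residents who leave.
2. **R-REM event counts:** use a negative binomial model with the same clustering terms. Do not add a days-in-residence offset where the recall window is fixed, as it is for the staff interview (two weeks).
3. **Any-positive staff-reported R-REM:** analyse it with the same mixed logistic model as the primary outcome, and state that it is a separate variable from the event count.
4. **Scope:** say whether the facility-clustered standard errors apply to the count models, and name the small-sample correction for 12 facilities.

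The cost is a distribution option and an offset in Proc Glimmix, a few sentences in the SAP, slightly wider intervals and some extra model-fitting work. The sample size does not change.
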